10.2. Adverse Events

AEs are defined as any untoward medical occurrence associated with the use of the investigational product in humans, whether or not considered related to the investigational product. An AE (also referred to as an adverse experience) can be any unfavorable and unintended sign (e.g., an abnormal laboratory finding), symptom, or disease temporally associated with any use of the investigational product, without any judgment about causality and irrespective of route of administration, formulation, or dose, including an overdose.

AEs will be mapped to preferred terms (PTs) and system organ classes (SOCs) using MedDRA dictionary version 22.0. Subjects experiencing the same event more than once will be counted only once at the most severe grade and the closest relationship to study treatment.

10.2.1. Treatment-emergent Adverse Events

An AE is defined as a treatment-emergent adverse event (TEAE) in the DB period if it meets one or more of the following criteria:

- An AE starting on or after the first study drug dose.
- An AE occurring prior to the first study drug dose that worsens (increase in grade) after the first study drug dose during Double-Blind period.
- An AE with a missing start date but with an end date after the first study drug dose date.
- Any AE started later than the 30 days of the last dose of study drug is not counted as a TEAE.

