8.4. Subject Withdrawal Criteria

Subjects who are discontinued from investigational product should be requested to continue with study visits until Month 60/EOS. Subjects who discontinue investigational product may be requested to come in for an Unscheduled Visit at the discretion of the Investigator depending on the timing of their next scheduled study visit.

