9.4.2. Blinding

Blinding is not applicable to this open-label, single-arm study.

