14.1.1.3. Treatment-Emergent Adverse Events

A TEAE is any event not present before the initiation of the investigational product in this study or any event already present, which worsens in either severity or frequency following exposure to the investigational product in this study.

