14.1.9. Follow-Up of AEs and SAEs

All AEs must be followed during the course of the study until the AE resolves, is no longer of clinical concern, has stabilized or is otherwise explained, or the subject is lost to follow-up.

AEs ongoing at the final visit that are deemed to be “possibly, probably, or definitely” related or of other clinical significance must be followed for as long as necessary to adequately evaluate the safety of the subject or until the event stabilizes, resolves, or is no longer of clinical concern. The Investigator must ensure that follow-up includes any supplemental investigations indicated to elucidate the nature and/or causality of the AE. This may include additional laboratory tests or investigations or consultation with other healthcare professionals, as considered clinically appropriate by the Investigator.

Drug-Induced Liver Injury or Disease Progression

All subjects showing possible DILI should be followed until all abnormalities return to normal or to the baseline state. DILI may develop or progress even after the causative drug has been stopped.

Cholecystitis or Pancreatitis

During the study duration, subjects will be instructed to contact the investigational site if they experience any of the following signs and symptoms: nausea, vomiting, abdominal pain, diarrhea, weight loss, fever, and chills, worsening or new fatigue, or weakness. Subjects will also be counseled to seek immediate medical assistance if they experience persistent severe abdominal pain.

If a subject is suspected to have acute pancreatitis or develops signs and symptoms consistent with acute pancreatitis, amylase and lipase levels should be monitored for 3 months after the onset of symptoms per standard of care. The Investigator should contact the Medical Monitor upon awareness. Results should be recorded promptly in the eCRF. Investigators should refer to standard-of-care guidelines on suspected pancreatitis ([Banks 2013](#), [Greenberg 2016](#)). Diagnosis of acute pancreatitis includes at least 2 of the following:

- Abdominal pain (acute onset of a persistent, severe, epigastric pain often radiating to the back)

- Serum lipase activity (or amylase) at least 3 times greater than the upper limit of normal
- Characteristic findings of acute pancreatitis on computed tomography or magnetic resonance imaging

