15.2. Determination of Sample Size

This is an estimation study with no formal hypothesis to be tested. Therefore, sample size is strictly based on number of subjects being captured from studies 747-213 and 747-214, or other Sponsor studies. The sample size in this study is not calculated based on statistical consideration.

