10.2.3. TEAE Analyses

All AE summaries will be restricted to TEAEs. Summaries that are displayed by SOC and PT will be ordered by descending order of incidence of system organ class and preferred term within each system organ class. Summaries of the following types will be presented:

- Overall summary of TEAEs
- Subject incidence of TEAEs and the total number of entries by MedDRA SOC and PT.
- Subject incidence of TEAEs by MedDRA SOC, PT, and highest severity. At each level of subject summarization, a subject is classified according to the highest

severity if the subject reported 1 or more events. AEs with missing severity will be considered severe for this summary.

- Subject incidence of TEAEs by MedDRA SOC, PT, and closest relationship to investigational product (Related/Not Related). Related AEs are those with relationships reported as “Definite,” “Probable,” or “Possible,” and unrelated AEs are those with relationships reported as “Unlikely” or “Not Related.” At each level of subject summarization, a subject is classified according to the closest relationship if the subject reported 1 or more events. AEs with a missing relationship will be considered related for this summary.
- Subject incidence of serious TEAEs and the total number of entries by MedDRA SOC and PT.
- Subject incidence of TEAEs leading to investigational product withdrawal or study discontinuation by MedDRA SOC and PT. This is a subset of the AEs where Action Taken with Study Treatment is checked as “Drug Withdrawn” or where “Subject Discontinued from Study” is checked.

The following listings will be presented by subject:

- All adverse events
- Serious adverse events (a subset of the AEs where serious is marked as “Yes”).
- Severe adverse events (a subset of AEs where severity is marked as “Severe”).
- Related adverse events (a subset of the AEs where relationship marked as “Definite,” “Probable,” or “Possible”).
- Adverse events leading to Study Drug Withdrawal or Study Discontinuation (a subset of the AEs where Action Taken with Study Treatment is checked as “Drug Withdrawn” or where “Subject Discontinued from Study” is checked).
- Adverse events leading to death.

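### The SAP's TEAE rule relies on a double-blind period this study does not have and adds a 30-day cut-off the protocol lacks, so adverse events with late off-drug onset enter no AE incidence table

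*SAP*

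**What the plan says.** SAP 10.2.1 states that "An AE is defined as a treatment-emergent adverse event (TEAE) in the DB period" if it meets at least one of four listed criteria:

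1. The AE starts on or after the first dose.
2. An AE from before the first dose worsens, by an increase in grade, within the double-blind period.
3. The start date is missing and the end date falls after the first dose.
4. An exclusion rather than a criterion: "Any AE started later than the 30 days of the last dose of study drug is not counted as a TEAE".

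SAP 10.2.3 adds that "All AE summaries will be restricted to TEAEs", and its serious-event table counts serious TEAEs only. SAP section 11 reports no difference between the protocol's analyses and its own.

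Protocol 14.1.1.3 counts any event that is new after the start of investigational product in this study, or one already present "which worsens in either severity or frequency following exposure to the investigational product in this study". It sets no end date. Protocol 15.3 and 15.3.1 name SAEs alongside TEAEs as things to be tabulated.

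On design, protocol 9.4.2 says "Blinding is not applicable to this open-label, single-arm study", and SAP 3.3 agrees.

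On follow-up, protocol 8.4 says "Subjects who are discontinued from investigational product should be requested to continue with study visits until Month 60/EOS". Section 7.4.3 keeps subjects with decompensation events in scheduled visits for safety, and section 8.4.1.1 encourages the same after severe related AEs. AEs are collected until participation ends (14.1.4.1), and SAEs in subjects who remain off drug must be reported (14.1.7).

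**The concern.** Long-term safety and tolerability is the primary objective, and the AE incidence tables are its main output. The protocol invests in off-drug follow-up to Month 60, in part for subjects who stopped because of hepatic decompensation or a severe related event. It also warns that "DILI may develop or progress even after the causative drug has been stopped". If the SAP is followed, new events in most of that follow-up are collected but never tabulated as AEs or SAEs.

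The rule also cannot be programmed unambiguously. The worsening criterion points to a period that does not exist, and the cut-off sits inside a list where meeting any one item is enough. Because SAP section 11 declares no deviation, a reader of the study report would not learn that the tabulated TEAEs differ from those the protocol defines.

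**Working it through.** There is no planned figure to reproduce. Protocol 15.2 says "This is an estimation study with no formal hypothesis to be tested", and the sample size has no statistical basis. The check is a comparison of definitions, followed by arithmetic for scale.

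**Definitions side by side**

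| Element | Protocol 14.1.1.3 | SAP 10.2.1 |
|---|---|---|
| Period | After first investigational product in this study | Double-blind period (none exists) |
| Worsening | Severity or frequency | Increase in grade only |
| Upper limit | None | Onset within 30 days of last dose |
| Tables built on it | TEAEs and SAEs (15.3, 15.3.1) | TEAEs only; SAE table is serious TEAEs (10.2.3) |

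**Tracing one event.** Take a new SAE two years after last dose in a subject still attending visits. It meets the first SAP criterion (onset after first dose), so it qualifies under the at-least-one rule. The fourth item then says it is not counted. Two programmers could produce different tables. If the exclusion governs, which is evidently the intent, the SAE appears in listings and in no AE incidence table. Under the protocol definition it is a TEAE.

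**Undefined term.** The SAP does not say whether last dose means the final dose or the last dose before an interruption. The footnote to protocol Table 4 allows restart only after at least 30 days, so the two readings can classify an event differently.

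**Scale for one subject.** Inputs: 60 months of follow-up (protocol 7.1.4), a 30-day window (SAP 10.2.1), and months of 365.25/12 days (SAP 5.4).

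Off-drug days = (60 − stop month) × 365.25/12; share inside the window = 30 / off-drug days.

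- Stop at Month 6: 54 × 30.4375 = 1643.6 days; 30/1643.6 = 1.8%
- Stop at Month 12: 48 × 30.4375 = 1461 days; 30/1461 = 2.1%; the other 1431 days (3.92 years) are outside
- Stop at Month 24: 36 × 30.4375 = 1095.8 days; 2.7%
- Stop at Month 48: 12 × 30.4375 = 365.25 days; 8.2%

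**Scale for the study.** N = 133 (protocol 7.2). The documents give no stopping rate, so 10-30% stopping with 2-3 further years of follow-up is an assumption.

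- Maximum follow-up: 133 × 5 = 665 person-years
- Low: 133 × 0.10 × 2 = 26.6 person-years; 26.6/665 = 4%
- High: 133 × 0.30 × 3 = 119.7 person-years; 119.7/665 = 18%
- Part inside the window: 13.3 × 30/365.25 = 1.1 and 39.9 × 30/365.25 = 3.3 person-years, leaving 25.5 and 116.4 outside

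**Sensitivity.** Assume instead a constant annual stop rate a, with everyone who stops staying to Month 60. With λ = −ln(1 − a), T = 5 and w = 30/365.25, the person-years outside the window are 133 × [(T − w) − (1 − e^(−λ(T−w)))/λ]. For a = 5%, 10% and 20% this gives about 76, 144 and 257, or 11%, 22% and 39% of 665. Under the protocol definition, none of this time is excluded.

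**The case against.** The strongest reply is that nothing is lost and much is still summarised.

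- All AEs are collected, and the SAP lists all, serious, severe, related and fatal events by subject.
- SAP 9.2 keeps post-discontinuation data in the exploratory time-to-event summaries, where MELD of 15 or more is the one component visible in the public text.
- SAP 10.3 summarises laboratory values, shifts and Hy's law cases with no post-dose limit.
- SAP 10.2.4 describes the special-interest summaries as covering both TEAEs and SAEs, which might admit late SAEs.
- Protocol 14.3 adjudicates hepatic and renal events after first dose without a cut-off, and the DMC sees a cumulative list of all SAEs (protocol 15.9).
- A 30-day window is conventional for an on-treatment table.

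All of this stands. A reader might infer that late events reach no table of any kind; the documents do not support that. The gap is in AE incidence tables.

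A reader might also infer that the tables will be selectively favourable because they drop the harm that made subjects stop. That does not follow either. Such harm starts on drug, counts as a TEAE and enters the table of TEAEs leading to withdrawal. The cut-off works on onset date, so an injury that begins on drug and progresses later remains a TEAE. Only new onset beyond 30 days is lost.

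Two smaller inferences are weak. Read literally, the second criterion admits no worsened event. However, protocol 14.1.1.1 treats worsening in severity or frequency as itself an AE, so worsening recorded with a new start date can qualify under the first criterion. The absence of an explicit anchor to this study in SAP 10.2.1 is minor, because SAP section 1 limits the plan to this protocol and SAP 5.1 anchors baseline to first dose in Study 977-311.

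None of this supplies an incidence table for late AEs and SAEs. The special-interest wording conflicts with the TEAE-only rule in SAP 10.2.3 and does not resolve it.

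**Conclusion.** The point holds within these limits. SAP 10.2.1 refers to a period that does not exist, narrows worsening to grade, and adds an undeclared 30-day limit in a list that contradicts itself. Together with SAP 10.2.3, it leaves AEs and SAEs of new onset more than 30 days after last dose out of every AE incidence table, with the special-interest SAEs uncertain. For a study whose primary objective is long-term safety, listings do not replace those tables.

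For a subject stopping at Month 12 and staying to Month 60, 97.9% of off-drug days (1431 of 1461) are outside the window. At study level the range is about 27-120 off-drug person-years (4-18% of 665), almost all outside it. This rests on assumed stopping and retention; the sensitivity scenario, with full retention to Month 60, gives more.

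No count of missing events should be attached. A reader might multiply these person-years by the 5.2 hepatic events per 100 patient exposure years in protocol Table 1. That rate is for subjects on OCA 10 mg and includes isolated biochemical elevations, so it does not describe off-drug time after the combination tablet.

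**What to change.** Before the SAP is used for any data snapshot:

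- Delete both references to a double-blind period in SAP 10.2.1.
- Use the protocol's TEAE definition: onset, or worsening in severity or frequency, after the first FDC dose in Study 977-311.
- Take the 30-day window out of the criteria list, state it as a separate on-treatment rule, and define last dose, including how interruptions are handled.
- Keep the 30-day tables. Add tables of AEs, SAEs, deaths and special-interest events from first dose to last study contact, split at 30 days after last dose.
- State whether SAP 10.2.3 or the special-interest text in 10.2.4 governs SAEs in those categories.
- Record any remaining difference from the protocol in SAP section 11.

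The cost is SAP wording and one extra set of AE tables from data already collected.

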10.2.2. Serious Adverse Events

An AE is considered “serious” if, in the view of either the Investigator or Sponsor, it results in any of the following outcomes:

- Death
- Is immediately life-threatening
- Requires in-patient hospitalization or prolongation of existing hospitalization
- Results in persistent or significant disability or incapacity
- Results in a congenital abnormality or birth defect
- Is an important medical event that may jeopardize the subject or may require medical intervention to prevent one of the outcomes listed above. Examples of such events are intensive treatment in an emergency room or at home for allergic bronchospasm; blood dyscrasias or convulsions that do not result in hospitalization; or development of drug dependency or drug abuse. Any malignancy is to be reported as a serious AE.

Events **not** considered to be SAEs are hospitalizations for:

- Routine monitoring of the studied indication and not associated with any deterioration in condition or AE
- Elective treatment for a pre-existing condition that did not worsen
- Respite care or observation when there is no AE associated with the hospitalization

10.2.3. TEAE Analyses

All AE summaries will be restricted to TEAEs. Summaries that are displayed by SOC and PT will be ordered by descending order of incidence of system organ class and preferred term within each system organ class. Summaries of the following types will be presented:

- Overall summary of TEAEs
- Subject incidence of TEAEs and the total number of entries by MedDRA SOC and PT.
- Subject incidence of TEAEs by MedDRA SOC, PT, and highest severity. At each level of subject summarization, a subject is classified according to the highest

severity if the subject reported 1 or more events. AEs with missing severity will be considered severe for this summary.

- Subject incidence of TEAEs by MedDRA SOC, PT, and closest relationship to investigational product (Related/Not Related). Related AEs are those with relationships reported as “Definite,” “Probable,” or “Possible,” and unrelated AEs are those with relationships reported as “Unlikely” or “Not Related.” At each level of subject summarization, a subject is classified according to the closest relationship if the subject reported 1 or more events. AEs with a missing relationship will be considered related for this summary.
- Subject incidence of serious TEAEs and the total number of entries by MedDRA SOC and PT.
- Subject incidence of TEAEs leading to investigational product withdrawal or study discontinuation by MedDRA SOC and PT. This is a subset of the AEs where Action Taken with Study Treatment is checked as “Drug Withdrawn” or where “Subject Discontinued from Study” is checked.

The following listings will be presented by subject:

- All adverse events
- Serious adverse events (a subset of the AEs where serious is marked as “Yes”).
- Severe adverse events (a subset of AEs where severity is marked as “Severe”).
- Related adverse events (a subset of the AEs where relationship marked as “Definite,” “Probable,” or “Possible”).
- Adverse events leading to Study Drug Withdrawal or Study Discontinuation (a subset of the AEs where Action Taken with Study Treatment is checked as “Drug Withdrawn” or where “Subject Discontinued from Study” is checked).
- Adverse events leading to death.

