15.3. Safety Analysis

The LTSE Population will be the primary population used for safety analyses.

Safety data, including SAEs, TEAEs, physical examinations, ECGs, vital signs, clinical laboratory assessments, and treatment discontinuations, will be assessed.

The incidence of TEAEs and SAEs will be tabulated by system organ class, preferred term, and severity.

All events of potential hepatic injury, suspected liver-related clinical outcomes, and potential renal injury that occur after administration of the first dose of the investigational product will be reviewed and adjudicated by independent adjudication committees ([Section 14.3](#)).

Laboratory parameters and vital signs will be summarized (including Hy's law) using descriptive statistics at baseline (defined as the last assessment performed before the first dose of investigational product in Study 977-311) and at each scheduled post-baseline visit in Study 977-311. The change from baseline will also be summarized. ECGs will be summarized using frequency at each visit. The shift from baseline will also be summarized.

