15.3.1. Adverse Events

AEs will be coded using the Medical Dictionary of Regulatory Activities (MedDRA). Summary tables of TEAEs will be provided. The incidence of TEAEs will be tabulated by system organ class and preferred term and by severity and relationship to treatment. Summaries of TEAEs leading to investigational product discontinuation and SAEs will be provided.

The incidence of TEAEs and SAEs will be tabulated by system organ class and preferred term and similarly by severity and relationship to treatment.

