11. DEVIATIONS FROM PROTOCOL

There have been no deviations between the protocol-defined statistical analyses and those presented in this statistical analysis plan.

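### The protocol promises SAE tables by severity and by relationship to treatment; the SAP plans serious events by SOC and PT only, yet declares no deviations

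*SAP*

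**What the plan says.** Protocol 15.3 states: "The incidence of TEAEs and SAEs will be tabulated by system organ class, preferred term, and severity". The synopsis says the same. Protocol 15.3.1 goes further: "The incidence of TEAEs and SAEs will be tabulated by system organ class and preferred term and similarly by severity and relationship to treatment". It also commits to a product-specific summary: "Summaries of TEAEs leading to investigational product discontinuation and SAEs will be provided".

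SAP 10.2.3 opens with a restriction: "All AE summaries will be restricted to TEAEs". SAP 10.2.1 sets the outer limit of that class: "Any AE started later than the 30 days of the last dose of study drug is not counted as a TEAE". Within it, SAP 10.2.3 plans tables by highest severity and by closest relationship for all TEAEs taken together. Serious events have a single table: "Subject incidence of serious TEAEs and the total number of entries by MedDRA SOC and PT". For discontinuation the plan is "Subject incidence of TEAEs leading to investigational product withdrawal or study discontinuation by MedDRA SOC and PT", triggered by either of two boxes on the AE form. SAP 11 then states: "There have been no deviations between the protocol-defined statistical analyses and those presented in this statistical analysis plan".

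**The concern.** Safety and tolerability are the primary objective, and the study has one arm and no comparator. A reader of the report will want to know how many subjects had a serious event that the investigator considered related, how severe the serious events were, and in which body systems they fell. The protocol says these will be tabulated. The SAP, which governs programming, does not include the tables and does not record the change.

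There is also a procedural consequence. SAP 1 says that analyses added to supplement those in the SAP will be labelled post-hoc in the study report. If the omission is found only when the report is written, tables that the protocol prespecified would carry that label.

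**Working it through.** No arithmetic applies: the study tests no hypothesis, and the point concerns which tables are planned. The current texts of the two documents compare as follows.

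| Output | Protocol 15.3 / 15.3.1 | SAP 10.2.3 |
|---|---|---|
| SAEs by SOC and PT | Promised | Serious TEAEs only |
| SAEs by severity | Promised, in both sections | Not specified |
| SAEs by relationship | Promised in 15.3.1 | Not specified |
| TEAEs leading to product discontinuation | Promised | Only pooled with study discontinuation |
| Statement on deviations | n/a | SAP 11: none |

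**Can another planned table supply the missing SAE breakdowns?**

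- *All-TEAE severity and relationship tables.* Serious TEAEs are included in them but cannot be separated out. Each subject is classed once per level, at the highest severity and the closest relationship. A subject with a serious unrelated event and a non-serious related event under one preferred term appears there as related. Severity behaves the same way.
- *Special-interest sections (SAP 10.2.4).* These give SAEs by SOC and PT only.
- *Overall summary of TEAEs.* Its rows are not specified. It may or may not contain a serious-and-related line.
- *Listings.* Serious, severe and related events are each listed by subject, so a hand count is possible. A listing is not the tabulated incidence that the protocol promises.

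**Which SAEs are covered?** The protocol names SAEs alongside TEAEs and sets no time limit. Protocol 8.4 asks subjects who stop product to continue visits to Month 60, and Protocol 14.1.7 requires their post-treatment SAEs to be reported. Under SAP 10.2.1 and 10.2.3, those starting more than 30 days after the last dose are collected and listed but enter no table.

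**What does pooling do to the discontinuation table?** Let A be the TEAEs marked *Drug Withdrawn* and B those marked *Subject Discontinued from Study*. The SAP tabulates A or B; the protocol promised A. The pooled set contains all of A, so its count equals or exceeds the promised one. The excess is the events in B but not in A, for example in a subject already off drug for another reason. The 30-day limit keeps that group small. The pooled table can over-include but cannot miss a product discontinuation.

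**The case against.** The best defence is that this is an omission of table shells in a descriptive study. All the fields are collected and the events are listed. Potential hepatic injury, liver-related outcomes and renal injury go to independent adjudication (Protocol 14.3). The DMC sees SAE narratives and a cumulative SAE list (Protocol 15.9). All of this stands, and it limits the harm. It does not supply the promised tables or make SAP 11 accurate.

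It can also be said that SAEs in Protocol 15.3.1 was shorthand for serious TEAEs. Even on that reading, the severity and relationship breakdowns are absent.

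A reader might infer that neither serious-event causality nor discontinuation can be read from any table. The documents do not support that. SAP 6 tabulates product discontinuation and study discontinuation separately, each with reasons, so overall product discontinuations by reason are available; only the SOC and PT detail is pooled. Nor are serious events absent from every severity or relationship table, since serious TEAEs enter the all-TEAE versions. What is missing is the breakdown specific to serious events.

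**Conclusion.** The mismatch is real and lies in current text. Two promised SAE breakdowns, by severity and by relationship, are not in the SAP. The SOC and PT table covers only the treatment-emergent part of the SAEs. SAP 11 is therefore wrong as written. The discontinuation table is a minor point, because the promised set is contained in the pooled one. The SAP should be changed, but no data are lost and no planned estimate is invalidated. The conclusion assumes that the unspecified overall TEAE summary was not meant to carry these breakdowns; a single row there would in any case not give them by SOC and PT.

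A reader might want to size the gap by projecting an SAE count from the parent studies. The documents do not support a usable figure. They report three SAEs in each study's first 6 months, in 75 and 72 subjects. If all gave the full 6 months, that is 6 / (147 × 0.5) = 8.2 per 100 subject-years, with an exact Poisson 95% interval of about 3.0 to 17.8. For 133 subjects followed an assumed 2.5 to 5 years on average, the extremes are 0.030 × 133 × 2.5 ≈ 10 and 0.178 × 133 × 5 ≈ 118. That range is too wide to be informative. It also assumes a constant rate carried over from mixed regimens to subjects selected for rollover. The point does not depend on it.

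**What to change.** 1. Add to SAP 10.2.3 two tables: SAEs by SOC, PT and highest severity, and SAEs by SOC, PT and closest relationship. Cover all SAEs after the first dose, with those starting more than 30 days after the last dose shown separately, and extend the existing SOC and PT table in the same way. Amend the sentence restricting all AE summaries to TEAEs so that it permits this. Adding serious-TEAE tables alone would still leave the late off-drug SAEs untabulated.
2. Restrict the discontinuation table to TEAEs with the action *Drug Withdrawn*, or add a row or table for them. A separate study-discontinuation table is optional, since the protocol does not promise one.
3. Correct SAP 11, or record and justify there any difference that is kept.

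The cost is about three tables. Seriousness, severity, relationship and both action fields are already collected. Making the change before database lock avoids the post-hoc label under SAP 1.
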